### **2.3.2 *Potential Benefits***

This trial may ascertain whether use of the RJ2 device provides a more effective way to support the jaw that reduces the incidence of TMD pain compared to the dental assistant supporting the jaw for patients having removal of 3rd molars.

### 3 OBJECTIVES

#### 3.1 Study Objectives

Primary: In patients undergoing mandibular 3rd molar extractions with moderate/deep sedation or general anesthesia, compare the incidence of TMD pain within a 6-month follow-up period between the two groups:

1. UC group, using a bite block and with hand support of the jaw, and
2. EC group, using a bite block and the RJ2 device to support the jaw.

The secondary objectives of this study are to:

1. Compare the incidence of TMD pain between UC and EC groups using an alternate assessment instrument to identify TMD pain within a 6-month follow-up period
2. Compare TMD pain intensity between the UC and EC groups within a 6-month follow-up period: at 1-, 3- and 6 months.
3. Compare TMJ noise, pain characteristics (e.g., location in temple or jaw, and occurrence with wide opening of mouth) and change in jaw pain since it started, within a 6-month follow-up period: at 1-, 3- and 6 months.
4. (Exploratory Objective) Describe the experiences of surgeons and dental assistants with the new device at mid-way through recruitment of patients and at the end of recruitment.

#### 3.2 Study Outcome Measures

##### 3.2.1 Primary

The primary outcome is the incidence of TMD pain within a 6-month follow-up period (binary dependent variable). TMD pain is deemed to have occurred if the patient's self report in the *Patient 1-, 3- and 6-month Follow-up Questionnaires* endorses either or both of the following questions: Pain in jaw with wide opening, or pain in temples, jaw joints or jaw muscles. The primary analysis will include all available follow-up measures (1, 3, and 6 months) for each patient to estimate the incidence of TMD pain.

##### 3.2.2 Secondary

1. The incidence of TMD pain, as measured with the validated *TMD Pain Screener Questionnaire* (binary dependent variable), will be compared between the UC and EC groups within a 6-month follow-up period based on patients' self report in the

*Patient 1-, 3- and 6-month Follow-up Questionnaire.*

2. TMD pain intensity, as measured with the validated *Characteristic Pain Index (CPI)* within a 6-month follow-up period (treated as a continuous measure), will be compared between the UC and EC groups based on patients' self report in the *Patient 1-, 3- and 6-month Follow-up Questionnaire*.
3. The UC and EC groups will be compared for TMJ noise, pain characteristics (e.g., location in temple or jaw, and occurrence with wide opening of mouth) and change in jaw pain since it started, within a 6-month follow-up period based on patients' self report in the *Patient 1-, 3- and 6-month Follow-up Questionnaire*.
4. A final secondary outcome is descriptive: a summary of the experiences of surgeons and dental assistants with the new RJ2 device at mid-way through recruitment of patients and at the end of recruitment based on their self report in the *Doctor Questionnaire Regarding Use of the Device* and *Dental Assistant Questionnaire Regarding Use of the Device*, respectively.

## 4 STUDY DESIGN

- **Study design**

This is a multicenter, two-arm, parallel RCT design in which approximately 294 patients undergoing 3rd molar (wisdom teeth) extraction will be randomized to either UC or EC, with data obtained at baseline, and at 1-, 3- and 6-months follow-up after surgery. Patients in the EC (study intervention) arm will undergo 3rd molar extraction with the RJ2 device supporting the jaw and concurrent use of a bite block. Patients in the UC (study control) arm will undergo 3rd molar extraction with the dental assistant supporting the jaw and concurrent use of a bite block.

The study will be conducted at the following sites:

- University of Minnesota School of Dentistry, Moos Tower, Oral Surgery surgical suite; [name].
- HealthPartners Como Clinic, Oral Surgery Department, [name]
- HealthPartners Eden Prairie Clinic, [name] [name], [name]
- Metro Dentalcare Specialty Center Burnsville, [name]

- **Study population**

Approximately 294 healthy (ASA 1 & II), consenting adult patients, age 18-30, requiring surgical removal of bilateral mandibular 3rd molars (concurrent maxillary 3rd molar removal allowed). All patients presenting to participating surgeons' practices for surgical removal of their 3rd molars will be considered for eligibility. See eligibility criteria described in Section 5.

Approximately seven (7) OMS will participate in the study. They represent three diverse practice settings; the University of Minnesota Dental School Department of Oral Surgery, HealthPartners (a large group practice) and a private practice setting. All surgeons are board certified and currently treat patients with 3rd molar extractions. Dental assistants at each of these sites will be invited to participate in the study.

- **Data Collection**

Patient-reported data will be collected via tablets, smart-phones, or computers at baseline during in-office visit(s) with the surgeons. To assist with in-office data collection, participating OMS will be offered tablets. OMS, dental assistants, and patients will provide baseline and follow-up data directly into the electronic data capture (EDC) system that is maintained by the HealthPartners Data Coordinating Center (DCC); data can be entered via tablets, smart-phones, or computers. After baseline, patient-reported data will be ascertained independent of office visits, and all follow-up patient, OMS and dental assistant data collection will be managed by HP DCC. Follow-up contacts to non-responders will also be managed by the DCC.

- **Overview of Study Schedule**

- The electronic data system used to collect patient and OMS/dental assistant data will be assessed for acceptability and compatibility prior to administration of any questionnaires.
- OMS and their office staff will receive study training from the Study Coordinator (SC), after which the OMS is authorized to begin enrolling study patients.
- An in-office patient log will be kept regarding the reason patients were excluded or declined to participate.
- Once the patient is screened using the *Screening Questionnaire* that comprises the inclusion and exclusion criteria, patients who are eligible will be invited to participate in the study. Potential patients who are interested in study participation will undergo consent procedures.
- Patients will complete these baseline forms and questionnaire before surgery: *Patient Contact and Patient Demographics information*, and *Patient Baseline Questionnaire*.
- Randomization procedures will occur, and patients will receive their randomized assignment.
- The OMS will complete the *Doctor Surgery Questionnaire* after completing the 3rd molar extractions.
- At 1, 3, and 6 months post-baseline, patients will complete follow-up assessments via an online questionnaire. Non-responders will be followed up with email, telephone, and/or texting. All patients will be followed up regardless of whether they report TMD pain at any follow-up.

- Midway through and at the end of the enrollment phase of the study, the OMS and dental assistants will complete a questionnaire regarding their experience with the use of the device.
- Approximately 3 months into recruitment, [name], [name], study engineers and OMS will meet to discuss their experience with using the device.

### **First Month Follow-up of Study Patients by study staff**

Patients will receive emails with active links to the online web-based *Patient One-month Follow-up Questionnaire* for electronic completion. The DCC will attempt email, telephone and/or text contact for non-responders to remind them to complete the questionnaires online or over the telephone. Completion of questions over the telephone is an option for those patients who do not complete the form by close of data collection window.

### **Months 3 and 6 Follow-up of Study Patients by study staff**

Similar procedures, as in the first month time point, will be repeated at months 3 and 6.

## 5 STUDY ENROLLMENT AND WITHDRAWAL

The target sample size for this study is 294 patients. To meet this target, we anticipate that 500 patients will need to be screened. Enrollment will include patients who present to the participating oral & maxillofacial clinics for surgical removal of mandibular bilateral 3rd molars (concurrent removal of maxillary 3rd molars is allowed). Each OMS will enroll no more than 60 patients into the trial.

### 5.1 Subject Inclusion Criteria

In order to be eligible to participate in this study, a **patient** must meet all of the following criteria:

- Between 18 to 30 years of age at time of enrollment;
- Willing to provide informed consent to be randomized to either using the device or not when having surgical removal of 3rd molars with moderate/deep sedation or general anesthesia;
- Requires surgical removal of bilateral mandibular 3rd molars with moderate/deep sedation or general anesthesia; concurrent maxillary 3rd molars removal allowed;
- American Society of Anesthesiologists (ASA) Physical Status category 1 (normal healthy patient) or Category 2 (patient with mild systemic disease);
- Available to be contacted for study purposes by e-mail, phone and/or text;
- Willing to provide contact information for one other person who will know the patient's whereabouts in the event the patient cannot be reached. This contact information must be different from the patient's contact information;
- Willing to comply with all study procedures and be available for the six month duration of data collection.

In order to participate in this study, **dental assistants** must meet all the following criteria:

- Holds a certification as a dental assistant
- Willing to provide informed consent according to their IRB requirements and procedures.

- Willing to comply with all study procedures.
- Willing to provide feedback on the device at the midpoint and end of the data collection.

In order to participate in this study, **OMS** must meet all the following criteria:

- Willing to provide consent according to their IRB requirements and procedures.
- Has the ability to receive emails and access online surveys.
- Willing to comply with all study procedures and be available for the duration of the study.
- Successfully completed a CODA certified program in advanced specialty education program in oral and maxillofacial surgery.
- Currently certified in moderate/deep sedation or general anesthesia.
- Currently certified in Advanced Cardiovascular Life Support (ACLS).

## 5.2 Subject Exclusion Criteria

**Patients** who meet any of the following criteria will be excluded from participation in this study:

- In the past 3 months, reports the presence of TMD pain in their temples, jaw joints or jaw muscles;
- Contraindication(s) for moderate/deep sedation or general anesthesia;
- Any condition or situation the surgeon determines that would prevent the patient from participating in this study;
- Inability to understand study procedures or provide consent in English;
- Device does not fit mandible;
- Supernumerary 3rd molars present.

### **5.3 Strategies for Recruitment and Retention**

All patients presenting to participating surgeons' practices will be considered for eligibility. For patients without TMD pain in the last 3 months, the surgeons or their office staff will discuss the study and review eligibility criteria with the patient. Patients who meet eligibility criteria and consent to participate in the study will complete their baseline data collection forms, undergo randomization procedures, and then have their 3rd molars surgically removed.

Patients will be told that their treatment will not be affected by participation in the study except that they will be randomized to UC or EC.

Patient retention is important to this study, and follow-up data will be collected independently of in-office visits. Study patients will be asked to complete follow-up assessments online at 1-, 3-, and 6- months after the baseline visit. Patients will be paid \$125 total for completed questionnaires; \$25 at baseline, \$25 at 1-month follow-up, \$25 at 3-month follow-up and \$50 at the 6-month follow-up.

Study patients will be contacted by email prior to each data collection time point at 1-, 3-, and 6-months post-surgery. The initial email contact for each survey period will contain the request to complete the questionnaire and an active link to the online web-based questionnaire. Email, telephone and/or text follow-up attempts will be implemented for non-responders. The HealthPartners DCC will email, call and/or text patients who do not complete the follow-up questionnaires by the close of the target data collection window to encourage them to complete surveys. When contacted, patients will be given the option to complete the questionnaire by telephone with the DCC.

### **5.4 Treatment Assignment Procedures**

The specific randomization procedure and methods are described below. Generally, participants will be randomized between the two study treatments, stratified by surgeon (7 surgeons and thus 7 strata total). This stratification addresses variation between surgeons in surgical technique and variation between practices in postoperative rehabilitation protocol.

#### **5.4.1 Randomization Procedures**

The OMS or dental assistant will provide a participant with the randomization assignment after the participant's eligibility is confirmed and his/her consent is obtained. The random assignment will be obtained from the study tablet used by the OMS or dental assistant. The study tablet, which will be programmed by the HP DCC, will (among other things) use randomized treatment assignments from a stratum-specific

(i.e., surgeon-specific) sequence of randomized assignments created as described in the following paragraph. Each surgeon-specific randomization sequence will be loaded into the tablet by the programmer at the HP DCC in such a way that it will be impossible for clinical study personnel, in particular for the OMS or dental assistant to access this sequence or to infer any treatment assignment in the sequence until the moment that assignment is given to a particular participant.

For each stratum (i.e., surgeon), the randomization sequence will be created by the project statistician using custom-written code in the R system (R Foundation for Statistical Computing, Vienna, Austria, <https://www.R-project.org/>), as follows: The sequence will use randomized permuted blocks of size 2 and 4, in each of which the two treatments are present equally often. The R code will first generate a random sequence of block lengths, so that study personnel will never be able to tell which block they are in, and then in each block, the treatment assignments will be randomly permuted, so that each sequence of possible treatments within a block is equally probable.

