#### **5.4.2 *Masking Procedures***

In this RCT, it is not feasible to blind patients, surgeons, or dental assistants to treatment after the intervention assignments have occurred, so they will not be blinded. It is, however, feasible to mask the sequence of treatment assignments until the moment each assignment is made, and this will be done, as described in Section 5.4.1, above.

The DCC will also be un-blinded to treatment arm assignment. However, study staff and investigators will not have access to any interim outcome data. Unmasking procedures during the surgery will not be necessary as the patient, surgeon, and dental assistants will be un-blinded to the treatment group for each patient. The patient's record in the OMS office will include documentation of study participation and their group assignment (i.e., UC versus EC).

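### Balanced blocks of 2 and 4 within each unblinded surgeon's sequence make roughly a tenth of assignments certain in advance, which Section 5.4.1 says cannot happen

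*Combined protocol and SAP*

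**What the plan says.** Section 5.4 stratifies by surgeon, with seven strata. Section 5.4.1 gives the block scheme: "The sequence will use randomized permuted blocks of size 2 and 4, in each of which the two treatments are present equally often". The order of the block sizes is random, and the purpose given for this is "so that study personnel will never be able to tell which block they are in". Within blocks, assignments are permuted "so that each sequence of possible treatments within a block is equally probable". The probability of each size is not given.

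The same section says the sequence is loaded on the tablet so that it is impossible for the surgeon or assistant to see it or "to infer any treatment assignment in the sequence until the moment that assignment is given". The assignment appears only after eligibility is confirmed and consent obtained.

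Section 5.4.2 says "it is not feasible to blind patients, surgeons, or dental assistants to treatment after the intervention assignments have occurred", and that the arm is noted in the patient's office record. Under Section 8.1 the study coordinator reviews the protocol, which contains the block sizes, at each surgeon's office.

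In Section 5.3 the surgeon or office staff review eligibility before randomization. Section 5.2 includes the exclusion "Any condition or situation the surgeon determines that would prevent the patient from participating in this study".

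**The concern.** Random block lengths hide block boundaries only some of the time. Because each sequence belongs to one surgeon and treatment is open, a surgeon's own past cases are the complete history of that sequence. Anyone who keeps a tally and knows the sizes can sometimes deduce the next assignment. Secure loading stops people reading the list, but it does not stop them counting.

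Foreknowledge matters if it can influence who is enrolled next. Here eligibility is settled before the assignment is shown, and one exclusion is at the surgeon's discretion. If patients expected to have difficult extractions were steered away from one arm, the groups would differ at baseline. The outcome is reported by unblinded patients. The primary analysis in Section 12.4 is unadjusted because randomization is expected to balance the groups.

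**Working it through.** The documents give no predictability figure to reproduce, only the absolute statements. The check derives the figure from the stated design.

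**Inputs**
- Block sizes 2 and 4, balanced, all orders equally probable (Section 5.4.1): 2 possible orders in a 2-block and 6 in a 4-block.
- Probability *q* that a block has size 4: not stated. Assumed 1/2, with a range of 1/3 to 2/3.
- 294 patients and 7 surgeons: 294/7 = 42 per surgeon on average. The cap is 60 (Section 5).

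**When an assignment is certain.** Every block starts with the arms level. A running difference of 2 can therefore arise only when a 4-block opens with two like assignments, and the next two must then be the other arm. This deduction does not need *q*.

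**Share that is certain.** Two of the six orders of a 4-block open with two like assignments, so a 4-block has on average 2 × 2/6 = 2/3 certain assignments. A 2-block has none. Mean block length is 2(1 − *q*) + 4*q* = 2(1 + *q*). The long-run share is (2*q*/3) / [2(1 + *q*)] = *q* / [3(1 + *q*)].

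| *q* | Long-run share certain | Simulated, 42 per surgeon |
|---|---|---|
| 1/3 | 1/12 = 8.3% | 8.0% |
| 1/2 | 1/9 = 11.1% | 10.7% to 10.8% |
| 2/3 | 2/15 = 13.3% | 13.0% |

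The simulations use an observer who knows the sizes and all past assignments but not the block boundaries. The share is slightly lower at 42 because the last block may be cut short. At *q* = 1/2, 0.107 × 294 = 31.5, so about 31 patients. About 92% of surgeons' sequences would contain at least one certain assignment. At 60 per surgeon the share is 10.9%.

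**Best guess.** The observer guesses the arm that is behind and tosses a coin when the arms are level.
- A 2-block gives 0.5 + 1 = 1.5 correct of 2.
- A 4-block gives 2.5 correct in the two orders that open with a like pair and 3 in the other four: (2 × 2.5 + 4 × 3)/6 = 2.83 of 4.
- At *q* = 1/2 this is (1.5 + 2.83)/(2 + 4) = 72%, and simulation agrees. With unpredictable allocation it would be 50%.

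**Alternative sizes.** Simulated at 42 per surgeon, with sizes equally likely within each scheme:

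| | 2 and 4 | 4, 6 and 8 |
|---|---|---|
| Certain in advance | 10.7% (about 31 of 294) | 2.3% (0.023 × 294 = 6.8, about 7) |
| Best guess correct | 72% | 68% |
| Mean end imbalance per surgeon | 0.2 patients | 0.5 to 0.6 patients |
| Variance cost | below 0.1% | below 0.1% |

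**Illustration of possible bias, on assumptions not in the documents.** Table 1's 132 per group corresponds to 28% against 14%. Take a control risk of 28%, with 30% to 50% of extractions difficult and 1.5 to 3 times the risk in difficult cases. Suppose every certain assignment were exploited perfectly: only easy cases in one arm and only difficult cases in the other. The bias is then the certain share times the risk gap.
- Smallest case (50% difficult, ratio 1.5): easy risk 0.28/(0.5 + 0.5 × 1.5) = 0.224, difficult 0.336. Bias 0.108 × 0.112 = 1.2 points.
- Largest case (30% difficult, ratio 3): easy risk 0.28/(0.7 + 0.3 × 3) = 0.175, difficult 0.525. Bias 0.108 × 0.35 = 3.8 points.

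The planned difference is 28 − 14 = 14 points. Partial exploitation of the certain assignments would give less. Steering on mere likelihood is not counted.

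**The case against.** The strongest reply concerns weight, not arithmetic. To exploit this, someone must know the sizes, keep a tally, foresee difficulty, and exclude or delay a patient already planned for surgery. The documents make knowledge of the sizes feasible but show neither tracking nor a motive. The plan also has safeguards: all presenting patients are considered, the assignment is released only after consent, and a log records why patients were excluded or declined. Surgeons record extraction difficulty and related factors, which are compared between arms and can enter an adjusted analysis (Section 12.4). Permuted blocks in open single-surgeon strata are always partly predictable, and larger blocks barely change ordinary guessing.

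Most of this stands and limits the point. The log and comparisons could help detect selection, but they do not prevent it, and the surgeon completes the surgery questionnaire after the operation knowing the arm. Release after consent does not help when the assignment could be deduced at the eligibility step. None of this makes the absolute statements in Section 5.4.1 true.

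A reader might also infer that the surgeon alone controls entry. The documents do not say so: office staff also review the criteria, possibly by telephone (Sections 5.3 and 7.1). Only the discretionary exclusion is expressly the surgeon's.

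**Conclusion.** The concealment claim in Section 5.4.1 is incorrect as written, and the design should be tightened. If the two sizes are equally likely, about 10.5% to 11% of assignments are certain in advance to anyone who knows the sizes and tracks one surgeon's cases. The range is about 8% to 13% for the values of *q* considered. One in nine is therefore not a fixed property of the plan: it is the long-run value under a probability the protocol does not state.

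A reader might go further and infer that allocation will be subverted or that the treatment comparison is biased. The documents do not support that. They establish an opportunity for selective enrolment, and the 1.2 to 3.8 points above are an illustration resting on outside assumptions and perfect exploitation.

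**What to change.** - Draw block sizes at random from 4, 6 and 8, and record their probabilities.
- Keep sizes and probabilities in a document held by the statistician, and remove them from the protocol and site materials. Sites can already know 2 and 4, so hiding the sizes without changing them would not be enough.
- Replace the absolute wording in Section 5.4.1. State that the list is concealed and the block sizes are withheld from sites, and that inference from past open assignments is reduced but not excluded.

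For sequences not yet used, certain assignments fall to about 2.3% and become hard to recognise without the sizes. The gain is mainly there, because an observer who knows the sizes still guesses right about 68% of the time.

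The cost is a small change to the R code, regenerated surgeon sequences and a protocol amendment. Mean end imbalance rises to about 0.5 to 0.6 patients per surgeon, with a variance cost below 0.1%. If enrolment has begun, only remaining assignments benefit, and leaving a block unfinished at the switch adds at most 2 to that surgeon's imbalance. The wording needs correcting even if the sponsor keeps its block sizes.
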